7. SAFETY ASSESSMENTS

People with chronic pain who begin completing frequent assessments of current pain, mood and activity levels may report increased awareness of their pain and distress. Participants will be told that such phenomena associated with close self-monitoring are a part of the treatment approaches we are offering, and will be addressed as part of the interventions. However, participants will be closely monitored (by the study coordinator/RA who will report relevant observations to the site PIs) during the study for significant increases in pain intensity and negative mood, and if any are noted, participants will be contacted to discuss these issues with the site PI. As appropriate, they will be referred by the site PI to their physician for further evaluation should there be any unexpected or significant deleterious changes. Participants will also be monitored as above during the course of the study for evidence of significant emotional problems. Any participant judged to be deteriorating significantly in terms of psychological and pain condition as a result of their participation in this study will be withdrawn from the trial and referred for individual treatment.

Therefore, a standardized referral form is not considered adequate for this study. The site PI will personally monitor all such referrals and document them accordingly. Such documentation will be kept confidential in the locked data storage area.

7.1 Specification of Safety Parameters

During the assessment phase, and/or during the treatment phase, should any participant report significant physical or emotional distress or other adverse event, the site PI will be notified immediately. The site PI will contact the participant by telephone, assess the event, and determine whether referrals to other healthcare providers are appropriate. Any necessary referrals will be made through telephone contact by the site PI to the appropriate practitioner.

7.2 Methods and Timing for Assessing, Recording, and Analyzing Safety Parameters

Diligent study safety monitoring will be conducted by the PIs on an ongoing basis, in conjunction with the IMC, the IRB and NCCIH as appropriate (see above). Study progress and safety will be reviewed weekly by the PIs. Progress reports, including patient recruitment into the full study, and adverse events (AEs) will be provided to the Independent Monitoring Committee (IMC) each quarter. This quarterly IMC progress report will be submitted to the IMC on January 15, April 15, July 15, and October 15. The more detailed semi-annual report will be submitted to the IMC on January 15 and July 15. A separate report will be compiled every 6 months and will include a list and summary of AEs. In addition, the report will address (1) whether adverse event rates are consistent with pre-study assumptions; (2) reason for dropouts from the study; (3) whether all subjects met entry criteria; (4) whether continuation of the study is justified on the basis that additional data are needed to accomplish the stated aims of the study; and (5) conditions whereby the study might be terminated prematurely. The IMC report prepared every 6 months will be signed by the members of the IMC and will be forwarded to the IRBs and NCCIH (reports will be provided more frequently on an ongoing basis if concerns are identified). The IRBs will review progress of this study on an annual basis.

Before the study begins, all subjects will be provided with contact phone numbers for research staff so that subjects can contact study staff at any time during the study. When in the laboratory, subjects will be supervised continuously. During the study, the PIs will monitor all adverse events, defined as any unfavorable or unintended symptom, sign or disease associated with a medical treatment or procedure that may or may not be related to the treatment or procedure. Part of this process will include monitoring of serial phone/online assessments by the research coordinator/RAs for worsening of physical or mental health during study participation. Adverse events can be related to participation in the study or to medical or psychiatric conditions being treated (e.g. depression), or they could be entirely unrelated to any of these (e.g., motor vehicle accident). In this study, we will use the FDA definition of serious adverse events (SAE; e.g., death, hospitalization, emergency room visits, suicide plans or attempts). SAEs will be systematically assessed at each lab visit. Any SAE, whether or not related to study intervention, will be immediately reported to the IRB and the NCCIH. Review by the IMC, IRB and NCCIH regarding the nature of the SAE will be used to decide whether the study should continue as is, whether changes to protocol are needed, or whether the study must be discontinued.

7.3 Adverse Events and Serious Adverse Events

To ensure the safety of trial participants, we will monitor all adverse events, defined as any unfavorable or unintended symptom, sign or disease associated with a medical treatment or procedure that may or may not be related to the treatment or procedure. Adverse events can be related to the treatment or to the disorder being treated (e.g. pain exacerbation), as well as to a concurrent disorder or treatment (e.g. diabetes or

its treatment), or they could be entirely unrelated to any of these (e.g., motor vehicle accident).

In this study, we will use the FDA definition of serious adverse events (SAE, e.g., death, hospitalization, emergency room visits, suicide plans or attempts).

A Serious Adverse Event (SAE) is any AE that results in one or more of the following outcomes:

- Death
- A life-threatening event
- Inpatient hospitalization or prolongation of existing hospitalization
- A persistent or significant disability/incapacity
- A congenital anomaly or birth defect
- Important medical event based upon appropriate medical judgment

7.4 Reporting Procedures

SAEs will be systematically assessed at each treatment session. Any SAE, whether or not related to study intervention, will be reported to the IMC and the IRB, as well as NCCIH on an ongoing basis. In addition, the PIs will prepare a semi-annual report on data collection and occurrence of any SAE for review by the IMC and IRBs. The initial SAE report will be followed by submission of a completed resolution report to the IRBs and the IMC.

Solicited events will occur as part of the weekly phone calls/online assessments during the treatment epoch.

Unsolicited events will occur when a participant contacts study staff to report a worsening in their symptomatology, and when pain and mood data during the intervention is compared to baseline.

SAEs that are unanticipated, serious, and possibly related to the study intervention will be reported to the IMC, IRB and NCCIH in accordance with requirements.

Unexpected fatal or life-threatening AEs related to the intervention will be reported to the NCCIH Program Officer within 7 days. Other serious and unexpected AEs related to the intervention will be reported to the NCCIH Program Official within 15 days.

Anticipated or unrelated SAEs will be handled in a less urgent manner but will be reported to the IMC, IRBs, NCCIH, and other oversight organizations in accordance with their requirements. In the annual AE summary, the IMC Report will state that they have reviewed all AE reports.

7.5 Follow-up for Adverse Events

In the event that a participant withdraws from the study or the investigator decides to discontinue a patient due to SAE, the patient will be monitored by the PIs via ongoing status assessment until (1) a resolution is reached (i.e., the problem has resolved or stabilized with no further changes expected), (2) the SAE is determined to be clearly

unrelated to the study intervention, or (3) the SAE results in death. Review by the IMC, IRB and NCCIH regarding the nature of any SAE will be used to decide whether the study should continue as is, whether changes to protocol are needed, or whether the study must be discontinued. In this case, the PI and Co-PI will discuss any proposed changes or study termination with the NCCIH Program Officer. We will also monitor safety alerts, defined as events that are relevant to the study populations and pose safety risks to study participants. Examples of safety alerts would include a sudden increase in pain symptoms or change in the type of pain experienced, or a clinically significant increase in patient depression or anxiety. Both SAEs and safety alerts will be tracked using a standardized form recording the date of the event, type of event, attribution of the event (e.g., judgment regarding whether it was intervention related), whether the event was resolved or controlled, and the resolution date. Any concerns identified will be reported to NCCIH and the IRB on an ongoing basis.

7.6 Safety Monitoring

Safety of participants will be ensured by the continued monitoring of their mental health and medical status. Subjects will all have access to treatment-as-usual services to address any study-induced adverse effects or other clinical concerns. We propose a Data Safety and Monitoring Committee (IMC) in which outside safety officers will oversee all implementation and data collection issues related to project safety in addition to careful IRB and PI monitoring. The IMC will be established external researchers who are experienced in the safe conduct of randomized controlled trials. They will monitor all data- and safety-related procedures and ensure participant safety during the study. The PIs will provide periodic updates (minimally, once per month) to the safety officers on study performance.

The proposed IMC is described in the DSMP document. All three monitors are not associated with this research project and thus work independently of the PIs, [name] and [name]. All three monitors are not part of the key personnel involved in this grant.

Study progress and safety will be reviewed quarterly (and more frequently if needed). Progress reports, including patient recruitment, retention/attrition, and AEs will be provided to the Independent Monitor(s) following each of the quarterly reviews. An Annual Report will be compiled and will include a list and summary of AEs. In addition, the Annual Report will address (1) whether AE rates are consistent with pre-study assumptions; (2) reason for dropouts from the study; (3) whether all participants met entry criteria; (4) whether continuation of the study is justified on the basis that additional data are needed to accomplish the stated aims of the study; and (5) conditions whereby the study might be terminated prematurely. The Annual Report will be sent to the IMC and will be forwarded to the IRB and NCCIH. The IRB and other applicable recipients will review progress of this study on an annual basis. The PIs will also send copies of signed recommendations and comments from the IMC to the NCCIH Program Officer within 1 month of each monitoring review.

8. INTERVENTION DISCONTINUATION

This study will be stopped prior to its completion if: (1) the intervention is associated with adverse effects that call into question the safety of the intervention; (2) difficulty in study recruitment or retention will significantly impact the ability to evaluate the study endpoints; (3) any new information becomes available during the trial that necessitates stopping the trial; or (4) other situations occur that might warrant stopping the trial.

Other potential reasons for early termination may include individual participant gross noncompliance (e.g., not responding to phone calls from staff, several cancellations of treatment appointments, no-shows to treatment appointments). Participants will also be discontinued if study investigators see a >25% worsening of baseline pain and mood during the MT or SMT treatments.

Participants will be monitored during the course of the study for evidence of significant deleterious physical, pain-related or emotional changes. In the event that a participant is judged by the research assistants and/or PIs to be deteriorating significantly in terms of pain and emotional condition as a result of their participation in this study, the team may decide to withdraw the subject from the trial and refer them for appropriate treatment. Participants will also be informed that should any unexpected or significant deleterious changes in their condition occur, that they immediately call [name] or [name] (PhD licensed clinical psychologists). Subjects will be given the office phone numbers of Drs [name] and [name] to ensure access to study staff. Drs. [name] and [name] will determine whether referrals to other healthcare providers are appropriate. Any necessary referrals will be made through telephone contact by the PIs to the appropriate practitioner. Therefore, a standardized referral form is not considered adequate for this study. The PIs will personally monitor all such referrals and document them accordingly. Such documentation will be kept confidential in the locked data storage area in Drs. [name]' or [name]'s office.

If a participant experiences a SAE, he/she will be discontinued in the study.

For the purposes of intent-to-treat analyses, we will make every effort to obtain scheduled follow-up assessments for all individuals failing to complete the study for any reason.

If NCCIH asks us to discontinue the study, we will discontinue all participants. If the study intervention is discontinued we will continue to follow participants for 1-month post intervention, with their permission. As planned for the follow up period, participants will be asked to rate their pain, function and mood.

There will be no cases of temporary discontinuation of treatment.

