6.2.6 Missed Evaluations

There is a 6-week window from baseline (visit 1) to the first lab session (visit 2). The first lab session (visit 2) must occur within this window and the second lab session (visit 3) must be within 2 weeks of the first. The first treatment visit (visit 4) is to

occur within one week from lab session 2 (visit 3).

If a participant misses an intervention session (MT or SMT) the staff will attempt to reschedule the visit for the following week, and the treatment schedule will be adjusted accordingly.

Treatment sessions 1-4 (visits 4-7) must all occur within 2 months of lab session 2 (visit 3). The first post-treatment lab session (visit 12) should occur within one month from treatment session 8 (visit 11).

The second post treatment lab session (visit 13) must occur within 2 weeks of the first post treatment lab session (visit 12).

The date of the follow-up assessments will be calculated from the date of the final post treatment lab session (visit 13). Participants will have a 2-week window around this date to complete the 3- and 6-month follow-ups (visits 14 & 15). Failure to complete these assessments within this window will result in the follow-ups being skipped.

All visits that fall outside of these allowable windows will be reported as protocol deviations.

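### Stopping rules do not separate ending treatment from ending assessment, and post-treatment EO visits are neither named for retention nor datable for participants stopped before session 8

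*Protocol*

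**What the plan says.** **Deterioration.** Section 7 says a participant judged to be deteriorating significantly because of the study "will be withdrawn from the trial and referred for individual treatment". Section 8, on essentially the same judgement, says "the team may decide to withdraw the subject from the trial". Section 8 also has a separate numerical rule: "Participants will also be discontinued if study investigators see a >25% worsening of baseline pain and mood during the MT or SMT treatments".

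**Serious adverse events.** Section 8: "If a participant experiences a SAE, he/she will be discontinued in the study". Sections 7.2 and 7.3 give emergency room visits as an example of a serious event and count adverse events unrelated to the study.

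**Retention.** Section 8 says that, for intent-to-treat purposes, "we will make every effort to obtain scheduled follow-up assessments for all individuals failing to complete the study for any reason".

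**Visit dates (Section 6.2.6).** "The first post-treatment lab session (visit 12) should occur within one month from treatment session 8 (visit 11"). Visit 13 must fall within 2 weeks of visit 12. "The date of the follow-up assessments will be calculated from the date of the final post treatment lab session (visit 13"). Any out-of-window visit is reported as a deviation, and months 3 and 6 are skipped if their 2-week window is missed.

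**Outcome and analysis.** The primary mechanism outcome is pre- to post-treatment change in EO function (9.5.1). EO is measured in the lab sessions, and its post-treatment value comes from visits 12 and 13 (6.1, 6.2.4). Section 9.6, under Aim 4, confirms that it is assessed only before and after treatment. The primary analysis is intent-to-treat (9.6), in everyone who completes baseline measures (9.3).

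**The concern.** Three pieces of conduct wording act on the same participants. The first makes withdrawal for deterioration compulsory in one section and optional in another, and does not distinguish stopping MT or SMT from leaving the study. The second promises continued data collection but, in the protocol's own vocabulary, covers visits that carry no EO measurement. The third gives a date for the post-treatment labs only if session 8 took place.

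Each visit pair gives one EO value, a placebo versus naloxone contrast, so a participant who misses visits 12 and 13 has no post-treatment EO value at all. The primary t-test then has no change score for that person, and the supplemental mixed model has no post-baseline EO observation. The participants affected would be those who worsened or had a serious adverse event, which makes the loss selective. They remain in the intent-to-treat sample as defined. An analysis plan can model such data but cannot recover what was never collected.

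**Working it through.** **1. Stopping rules compared**

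| Trigger | Section | Consequence |
|---|---|---|
| Significant study-related deterioration | 7 | withdrawal from the trial, compulsory |
| Essentially the same judgement | 8 | withdrawal from the trial, optional |
| More than 25% worsening of pain and mood | 8 | discontinued, compulsory; from what is not stated |
| Serious adverse event | 8 | discontinued in the study, compulsory |

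The first two rows conflict. The third is a separate criterion. None of the four says whether assessments go on.

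**2. What follow-up means in this protocol.** The Précis lists post-treatment assessments and 3- and 6-month follow-up assessments as separate items. The schedule in 6.1 has separate Post and Follow-up columns. Section 6.2.5 labels visits 14 and 15 as the follow-ups, and 6.2.6 dates the follow-up assessments from visit 13. Quantitative sensory testing appears in the schedule at visits 2, 3, 12 and 13 and not at months 3 or 6. On that usage, the retention sentence secures no EO data.

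**3. Dates.** The chain is session 8 → visit 12 → visit 13 → months 3 and 6. Section 6.2.6 reschedules a missed session but has no rule for a permanent stop. For someone stopped at session 4, for example, the first link is missing and so is every later date. The one-month contact in Section 8 follows the sentence on NCCIH stopping the study and covers ratings of pain, function and mood only.

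**4. The protocol's own figures.** Inputs from 9.2: 120 per arm, SD 7.5, limits ±3.0, alpha 0.05 per side, true difference 0.

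- Standard error = 7.5 × √(2/120) = 0.968.
- Normal approximation to power = 2Φ(3.0/0.968 − 1.645) − 1 = 0.854. The exact t calculation gives 0.851, matching the table.
- Enrolment = 240/(1 − 0.16) = 286. Budgeted loss = 286 − 240 = 46 (16.1%).

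If early stops fall within those 46, the planned power of 0.851 is unchanged.

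**5. Possible bias (illustration only).** Let p be the share of an arm with no post-treatment EO value, and g the mean EO change in the missing minus that in the observed. The observed arm mean is the full mean minus p × g, so the arm difference is biased by

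−(p₁g₁ − p₂g₂).

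The protocol gives neither p nor g. Suppose g is the same in both arms and the shares differ by up to 5 percentage points (0.05 × 143 ≈ 7 participants):

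| Net share × gap | Bias (points) | Share of the 3.0 limit | Chance of declaring equivalence at a true difference of 3.0, bias toward zero |
|---|---|---|---|
| 0 | 0 | 0% | 0.050 |
| 0.02 × 7.5 | 0.150 | 5.0% | 0.068 |
| 0.05 × 3.75 | 0.188 | 6.2% | 0.073 |
| 0.05 × 7.5 | 0.375 | 12.5% | 0.104 |

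The same 0.375 away from zero lowers that chance to about 0.02. Nor is 0.375 a ceiling. With equal shares of 0.05 and gaps of opposite sign, the bias is 0.05 × 7.5 − 0.05 × (−7.5) = 0.75. With equal shares and equal gaps it is 0.

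**The case against.** The retention sentence is expressly tied to intent-to-treat analysis. The primary analysis is intent-to-treat and its outcome is EO change, so a sympathetic reader would include the labs. The Précis also uses the term loosely, since the 240 said to complete follow-up are the 240 behind the pre-post power calculation. That shows intent and softens the point, but it does not name the visits, and the schedule's labels point the other way.

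Session 8 is not a gate either: 5.4 and 9.3 accept 6 of 8 sessions, and a late lab is only a deviation. This stands. A site may hold visits 12 and 13 for an early stopper, but the protocol gives it no date.

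Withdrawing someone thought harmed by the study, rather than exposing them to naloxone, ischemic, heat and cold pain, is a defensible safety choice. The fix has to respect that.

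A reader might infer more than the text supports:

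- **That EO data may not be collected after a stop.** No sentence says so.
- **That the rule on more than 25% worsening contradicts the deterioration rules, or that 7.5 sets a rival rule for serious adverse events.** The first is a separate criterion. In 7.5, "the investigator decides to discontinue a patient due to SAE" is part of a clause on monitoring after discontinuation.
- **That missing values could be imputed only from baseline EO.** Section 9.6 sets no such limit. Weekly questionnaires, spinal stiffness and baseline CPM would also be available.
- **That months 3 and 6 being skipped harms the primary outcome.** EO is not measured there.

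**Conclusion.** The point holds as a defect of conduct wording. Sections 7 and 8 conflict on withdrawal for deterioration. The rule on serious adverse events does not separate treatment from assessment. The retention sentence does not name the visits that carry the primary outcome. The date chain fails for anyone stopped before session 8. Followed literally, these together risk selective loss of the only post-treatment EO value in participants who worsened or had a serious adverse event.

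The number affected, any imbalance between arms, and the size and direction of bias cannot be derived from the protocol. The figures of 0 to 0.375 points and 0.050 to 0.104 rest wholly on assumed shares and gaps and on bias toward zero; they illustrate and do not bound. A reader might also infer lost power, but none is shown while stops stay within the budgeted 46. This is a cheap improvement and not a demonstrated threat to the primary result.

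**What to change.** 1. **Sections 7 and 8:** use one rule. A participant judged to be deteriorating significantly because of the study, meeting the criterion of more than 25% worsening, or having a serious adverse event stops MT or SMT and is referred as needed. Assessments continue unless the participant withdraws consent. Remove the two phrases that withdraw such participants from the trial.
2. **Section 8, retention sentence:** extend it to the post-treatment labs (visits 12 and 13) as well as the follow-up assessments, with naloxone and pain testing only where the site PI judges them safe.
3. **Section 6.2.6:** for participants who stop early, date visit 12 from the planned date of session 8, and months 3 and 6 from the planned date of visit 13 if that visit does not take place.

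**Cost:** a protocol amendment approved by both IRBs (11.1), with any matching consent change, and a few lab visits in participants who have stopped treatment. Because labs would be held only where judged safe, some of the participants of most concern would still lack EO data, so the change reduces selective missingness but does not eliminate it.
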